8.6.3 Duration of Response

DOR is defined as the time in months from date of the first documentation of objective response (CR or PR) per RESIST 1.1 to the first documentation of progression of disease or to death due to any cause in the absence of documented progression of disease (i.e., min [progression of disease date, death date] – date of the first observation of objective response +1) divided 30.4375. DOR will only be calculated for the subgroup of patients achieving a BOR of CR or PR.

The censoring rules to be applied to DOR are the same as for PFS.

8.6.4 Progression Free Survival

PFS is defined as the time from the first dose of study drug to the date of progression of disease or death (event) due to any cause, whichever occurs first. PFS (in months) will be calculated as:

(first event/censored date – first dose date of study drug +1)/30.4375.

The clinical progression without further radiological assessment as corroboration will not be considered as progressive disease.

Using iRECIST, PFS is defined as the time from the first dose of study drug to the date of death or the of first documented tumor progression (iUPD) provided that iCPD is confirmed at the next assessment, whichever is earlier.

The patients who have not progressed or died at the time of analysis will be censored. Following censoring rules will be applied for PFS:

Patients with no disease assessment (or only have assessment(s) with response = NE) after first study treatment or have baseline or post-baseline assessments where the RECIST criteria cannot be applied (e.g. not all baseline lesions assessed) will have their PFS time censored on the date of first dose with duration of 1 day unless they die within 2 tumor assessments of baseline, then they will be treated as an event with date of death as the event date.

Event time will be censored on the date of the last evaluable assessment documenting absence of progression of disease for:

- Patients on-study and progression-free at the time of analysis;
- Patients who have progression of disease or death on study after ≥2 consecutive missed tumor assessments;
- Patients given alternative cancer treatment prior to progression of disease or death on-study.

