#### 4.4.2. Missing assessments and inevaluable designation

When no imaging/measurement is done at all at a particular time point, the patient is not evaluable (NE) at that time point. If only a subset of lesion measurements are made at an assessment, usually the case is also considered NE at that time point, unless a convincing argument can be made that the contribution of the individual missing lesion(s) would not change the assigned time point response. This would be most likely to happen in the case of PD. For example, if a patient had a baseline sum of 50 mm with three measured lesions and at follow-up only two lesions were assessed, but those gave a sum of 80 mm, the patient will have achieved PD status, regardless of the contribution of the missing lesion.

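### The Day 1 censoring rule for progression-free survival can, as worded, be triggered by one incomplete scan, and it does not work when reused for duration of response

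*SAP*

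**What the plan says.** SAP 8.6.4 introduces its censoring rules with "The patients who have not progressed or died at the time of analysis will be censored". The Day 1 rule follows and names two groups, joined by *or*:

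- "Patients with no disease assessment (or only have assessment(s) with response = NE) after first study treatment";
- those who "have baseline or post-baseline assessments where the RECIST criteria cannot be applied (e.g. not all baseline lesions assessed").

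Both groups "will have their PFS time censored on the date of first dose with duration of 1 day". The one exception is "unless they die within 2 tumor assessments of baseline, then they will be treated as an event with date of death as the event date". Documented progression has no exception.

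A second rule follows: "Event time will be censored on the date of the last evaluable assessment documenting absence of progression of disease". It covers patients who are progression-free at the analysis, patients whose progression or death comes after two or more consecutive missed assessments, and patients given another cancer treatment first. No order of precedence between the two rules is given.

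SAP 8.6.3 starts DOR at the first response and adds: "The censoring rules to be applied to DOR are the same as for PFS". Its formula takes the earlier of progression and death as the end date and has no term for a censored date.

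Protocol Appendix 1 (RECIST 1.1, section 4.4.2) treats a scan with only some lesions measured as usually NE at that time point. The exception is where the missing lesion could not change the response, and of that exception it says: "This would be most likely to happen in the case of PD". Table 1 of the same appendix assigns PD whenever a new lesion appears, and allows PR or SD when not all non-target lesions were evaluated.

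**The concern.** The first group is limited by *only*; the second has no such limit. A programmer following the text could flag any patient with one incompletely read scan and set PFS to 1 day censored, whatever the other scans show.

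PFS (by RECIST 1.1 and by iRECIST) and DOR are secondary endpoints in both phases. They are reported as Kaplan-Meier medians and as 12- and 24-month rates (SAP 10.5.3.2 and 10.5.3.3). The chance of at least one incomplete scan rises with the number of scans, so the rule would fall hardest on the patients followed longest, responders among them. That is informative censoring at time zero. SAP 10.5.2.3 plans no sensitivity analysis that could reveal it, and Phase 2 cohorts start at about 15 patients, where a few reassignments matter.

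**Working it through.** **Inputs**

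- PFS formula (SAP 8.6.4): (event or censoring date - first dose + 1) / 30.4375.
- DOR formula (SAP 8.6.3): (end date - first response + 1) / 30.4375.
- Scan schedule (protocol 6.2.1): Weeks 8 and 16, then every 12 weeks, each ±7 days. With first dose on Day 1, Weeks 8, 16, 28 and 40 fall on Days 57, 113, 197 and 281.
- Share of scans that miss a baseline lesion: not in the documents. Assumed 5%, range 3% to 10%.

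**The plan's own figure.** First dose - first dose + 1 = 1 day, or 1 / 30.4375 = 0.033 months. It reproduces.

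**An illustrative patient.** PR at Week 8, confirmed at Week 16, one incomplete scan at Week 28, PD at Week 40.

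| | Incomplete scan is NE at that visit only | Second clause taken literally |
|---|---|---|
| PFS | 281 - 1 + 1 = 281 days, 9.23 months, event | 1 day, censored |
| DOR, first-dose date as end date | 281 - 57 + 1 = 225 days, 7.39 months, event | 1 - 57 + 1 = -55 days, -1.81 months |
| DOR, 1-day duration carried over | as above | 1 day, censored |

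With the ±7-day window, the negative DOR runs from 1 - 50 + 1 = -48 days (-1.58 months) to 1 - 64 + 1 = -62 days (-2.04 months). A first response at Week 16 gives 1 - 113 + 1 = -111 days (-3.65 months). If the first-dose date is used, every scheduled response date gives a negative value.

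**How many patients could be exposed.** For *k* independent scans, each incomplete with probability *q*, the share with at least one incomplete scan is 1 - (1 - *q*)^*k*. For *k* = 4:

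- *q* = 3%: 1 - 0.97^4 = 11.5%
- *q* = 5%: 1 - 0.95^4 = 18.5%
- *q* = 10%: 1 - 0.90^4 = 34%

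**The narrower reading.** Suppose the clause means patients with no evaluable baseline or no evaluable post-baseline assessment, with evaluability judged under Appendix 1. The illustrative patient then keeps 281 and 225 days. A confirmed responder has evaluable scans by definition, so none would meet the Day 1 rule and no negative DOR could arise.

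**The case against.** The best defence is context. The clause belongs to a sentence about patients without usable scans, and it says *assessments* in the plural. Its test is that RECIST cannot be applied; incomplete lesion assessment is only an example. If a partial scan establishes PD, RECIST has been applied and the test is not met. On that view the Day 1 rule and the last-evaluable-assessment rule fit together. The lead-in also confines censoring to patients without an event.

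The contextual argument stands as a plausible account of intent, but the text does not state that intent. On the narrow reading the post-baseline half of the clause adds little, because partly measured scans are usually NE and patients with only NE scans are already covered. The example chosen is also one where Appendix 1 can still yield PR, SD or PD. The lead-in is weak protection: the same list censors progression or death after missed assessments, and the early-death exception implies that later deaths are overridden.

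Three further objections stand in full:

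- The -55 days arises only if the first-dose date, not the 1-day duration, is carried into DOR.
- The incomplete-scan rate is assumed, and scans are taken as independent. The calculation also counts incomplete scans on which PD could still be called.
- All analyses are descriptive, and cohort expansion decisions rest on ORR (SAP 6.2).

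**Conclusion.** Wrong as written. Followed literally, the second clause gives a wrong PFS for a patient with one incomplete scan among evaluable ones, and nothing in 8.6.4 settles which rule prevails. The DOR cross-reference fails either way under that reading: it gives a negative duration or a 1-day duration with no meaning. *Within 2 tumor assessments of baseline* also has no defined counterpart for an endpoint that starts at response.

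A reader might go further and infer that the SAP necessarily discards documented progressions and will report negative DORs. The documents do not support that: the narrower reading is open, would spare confirmed responders, and may be what was meant. Nor does the 18.5% forecast how many patients will be lost. It illustrates exposure for patients with four scans under an assumed rate, and no effect on a PFS or DOR estimate has been calculated. The consequence is confined to descriptive secondary endpoints; the primary ORR is unaffected.

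**What to change.** In SAP 8.6.4, restrict Day 1 censoring to patients with no evaluable baseline or no evaluable post-baseline assessment, keeping the early-death exception. Add that an incomplete assessment is NE at that visit only, unless Appendix 1 (section 4.4.2 and Table 1) still allows a response or PD to be assigned, and that all other visits stand.

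In SAP 8.6.3, replace the cross-reference with a rule for DOR: censor at the last evaluable assessment on or after the first response, with the same missed-assessment and new-therapy rules. Add the censored date to the DOR formula.

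The cost is a few SAP sentences and the matching program logic. No new data are needed, and SAP 4.0 already provides for an updated SAP to be approved before database lock.

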8.6.5 Overall Survival

The overall survival (OS) is defined as the time from first dose of study drug to the date of death due to any cause. OS (in months) is calculated as (date of death – date of first dose of study drug +1) divided by 30.4375. Patients who are continuing on study at the time of an analysis, are lost to follow-up or who withdraw consent, will have their event time censored on the last date that they were known to be alive. The last date that patients are known to be alive can be derived from the clinical database and may include the latest Visit date for patients still on study or the latest Date of Contact on the Long-Term Follow-Up/Survival Status CRF page, whichever occurs latest. For patients with no follow-up after first dose of study drug, OS will be censored at the date of first dose.

8.7 Study Drug Exposure Variables

The exposure for KY1044 and Atezolizumab will generally be presented separately but in addition, the study treatment duration will be presented combining both treatments (please see below).

8.7.1 Study Treatment Duration

Study treatment duration (weeks) for each study drug separately is defined as ((last dose date+21 days – first dose date)+1)/7. For patients in the combination arm, an additional duration of study treatment will be calculated using the same formula but which takes the latest KY1044 or Atezolizumab administration for the last dose date, and the earliest of either drug for the first dose date.

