# 5.3 Treatment Duration

All patients treated with either KY1044 as single agent or in combination with atezolizumab will begin study treatment on Cycle 1 Day 1. Each cycle will consist of 21 days ( $\pm$ 3 days). The next scheduled dose (as single agent or in combination) may be delayed by up to 7 days to recover from previous Aes. If the next dose (as single agent or in combination) cannot be administered within the above mentioned 7-day delay, then the dose should be skipped. Dosing will resume at the scheduled dose or the next lower dose. Dose modifications should follow Section 5.6.

If more than one consecutive dose of KY1044 as single agent or in combination with atezolizumab has to be skipped due to study treatment-related toxicities, then the default position is that IMPs should be permanently discontinued. However, if a patient who misses more than one consecutive dose due to a study treatment-related toxicity experiences clinical benefit, and in the opinion of the Investigator it is in the patient's best interest to remain on study, then the patient may continue treatment after discussion with the Medical Monitor.

A patient may continue treatment with KY1044 as single agent or in combination with atezolizumab within this clinical study, as long as they are continuing to derive benefit from treatment, until the patient experiences unacceptable toxicity or confirmed disease progression per iRECIST. Patients will not be withdrawn from the study due to progressive disease per RECIST 1.1, unless clinically indicated.

Criteria for treatment cessation or patient withdrawal from the study are outlined in Section 8, and management of toxicities is outlined in Section 5.6.

Patients with SD, PR, unconfirmed CR, and unconfirmed progressive disease will continue treatment in additional cycles.

Patients who meet the following criteria will NOT continue treatment in additional cycles:

- Patients who experience unacceptable toxicity.
- Patients with confirmed progressive disease. These patients will enter the Safety follow-up period unless the Investigator considers it to be in the patient's best interest to remain on the study, and after discussion with the Medical Monitor.

• Patients with an unconfirmed progressive disease who show signs of clinical deterioration or toxicity. These patients will enter the Safety follow-up period, and will continue to be followed-up until confirmed progressive disease or initiation of a new treatment.

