#### Table 6-2:Phase 2 Assessments

Visit name	Screening	Cycle 1 (21 days; study Day 1-21; Week 1-3)			Cycle (21 da Week	2 ys; study 4-6)	y Day 22	-42;	Cycle (21 da Day 4 Week	3 ays; stud 13-63; 1 7-9)	ły	Cycle 4 (21 days) Cycles uj months (	) and all p to 48 4 years)	EOT u (up to 21 days after the last study dose)	Safety follow-up visit (90 days after the last study dose)	
Day of cycle	-28 to -1		CIDI	C1D8	CID15	- ALCO	1070	C2D8	C2D15	HUED	Ideo	C3D8	C4D1	and CXD1		
		pre-dose	post-dose			pre-dose	post-dose			pre-dose	post-dose		pre-dose	post-dose		
Obtain Informed Consent	x															
Obtain pharmacogenomic informed consent	x															
IXRS	x	Xª				Xª				Xª			Xa		х	
Demography	x															
Inclusion/ exclusion criteria	x	х														
Medical History b	х															
Height	х															
Weight	х	х				х				х			х		x	
Physical examination e	х	х				х				х			х		x	
Vital signs d	x	х	х			х	х			х			х		х	
ECOG performance	x	х				х				х			х		x	
Oxygen saturation test	x															
Cardiac markers e	х															
12-Lead ECG f	x	x	x							х	х				x	

Property of the Sanofi Group - strictly confidential

PAGE 97 OF 217

## Amended Clinical Trial Protocol 07

KY1044/SAR445256-KY1044-CT01/TCD17370 - alomfilimab

10-Nov-2021 Version number: 1

Visit name	Screening	Cycle 1 (21 days; study Day 1-21; Week 1-3)			Cycle (21 da Week	2 ys; study 4-6)	y Day 22	-42;	Cycle (21 da Day 4 Week	3 ays; stud 13-63; 17-9)	ly	Cycle 4 (21 days) Cycles uj months (	) and all p to 48 4 years)	EOT u (up to 21 days after the last study dose)	Safety follow-up visit (90 days after the last study dose)	
Day of cycle	-28 to -1		CIDI	C1D8	CID15	- C2D1		C2D8	C2D15	Max	Ideo	C3D8	C4D1	and CXD1		
		pre-dose	post-dose			pre-dose	post-dose			pre-dose	post-dose		pre-dose	post-dose		
Review AE	х	х	Х	х	х	х	х	Х	Х	х	х	х	х	х	x	х
Review Concomitant Medications	х	х				х				х			х		x	Х
Hematology	х	Xg		Xg	Xg	Xg		Xg	Xg	Xg		Xg	Xg		x	
Clinical Chemistry	х	Xg		Xg	Xg	Xg		Xg	Xg	Xg		Xg	Xg		x	
Fasting lipid profile h	х															
Coagulation (aPTT, INR)	х	X				Xg				Xg			X g		x	
HbA1c i	х														x	
Urinalysis j	х	х				х				х			х		x	
Pregnancy test k	х	х				х				х			х		х	
Thyroid function 	х									х					x	
Viral testing, HIV, HBV, HCV m	х															
Auto-Abs n	х					х							х		х	

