8.7.5 Dose Intensity

Absolute dose intensity (mg/week) is calculated as cumulative dose received (mg) / study treatment duration (weeks).

Relative dose intensity is calculated as the cumulative dose received (mg) / initial planned cumulative dose (mg). Initial planned cumulative dose is calculated as the starting dose (Cycle 1 Day 1 dose) multiplied by the scheduled number of administrations within the study treatment duration.

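### The SAP's treatment-duration formula counts one day too many, which slightly understates absolute dose intensity, and the SAP leaves the planned-dose count undefined

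*SAP*

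**What the plan says.** SAP 8.7.1 gives the duration for each drug, in weeks, as "last dose date+21 days – first dose date)+1)/7" (two opening brackets precede the quoted words). For the combination arm, "an additional duration of study treatment will be calculated using the same formula", running from the earliest first dose to the latest last dose of either drug.

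SAP 8.7.5 uses the duration twice. Absolute dose intensity is cumulative dose in mg divided by duration in weeks. Relative dose intensity is cumulative dose divided by the planned cumulative dose, which is the Cycle 1 Day 1 dose "multiplied by the scheduled number of administrations within the study treatment duration". The SAP does not say how that number is to be counted.

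Protocol 5.3 states "Each cycle will consist of 21 days", with a tolerance of 3 days either way. Protocol Table 6-2 labels the first cycle "Cycle 1 (21 days; study Day 1-21; Week 1-3", so Day 22 is Day 1 of Cycle 2. Protocol 2.2.1 and 2.2.2 place dose intensity in the Phase 1 primary tolerability endpoint and among the Phase 2 secondary endpoints. SAP 10.3.1 tabulates both the absolute and the relative version.

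**The concern.** Adding 1 is right when days are counted inclusively between two observed dates, as the SAP does for overall survival, progression-free survival and duration of response. In 8.7.1 the 21 days credited to the last dose already include the dosing day. The further 1 therefore takes in the date on which the next dose would fall due.

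Two quantities inherit this. The denominator of absolute dose intensity is a day too long for every patient, and the shortfall is proportionally largest in those who stop early. A Phase 1 dose level with more early stopping would thus look slightly less intensively dosed for a purely arithmetical reason. The window for counting planned doses can also reach a dose that the patient never had reason to receive, depending on how the count is programmed.

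**Working it through.** **Inputs.** Duration formula: SAP 8.7.1. Cycle length 21 days, Cycle 1 being Days 1 to 21: Protocol 5.3 and Table 6-2. Dose-intensity definitions: SAP 8.7.5. Atezolizumab 1200 mg every 3 weeks and the 3-day window: Protocol Table 5-1. About 70 cycles at most: Protocol 3.4.

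**The plan's own figure.** The documents contain no worked duration. The nearest stated figure is 21 days for one cycle. With a single dose on Day 1 the formula gives (1 + 21 − 1) + 1 = 22 days, so that figure is not reproduced. Dropping the final 1, or crediting 20 days in place of 21 and keeping the 1, each gives 21 days.

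**General case.** With n on-schedule doses the last falls on Day 21(n−1)+1, and the formula gives 21(n−1) + 21 + 1 = 21n + 1 days.

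**Absolute dose intensity.** Reported value over correct value = 21n/(21n+1). For atezolizumab, mg/week = 1200n ÷ ((21n+1)/7) = 8400n/(21n+1), against a correct 400.

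**Relative dose intensity, on-schedule patient with nothing missed.** Due dates are Days 1, 22, 43 and so on; Days 1 to 21n+1 contain n+1 of them, so a date count gives n/(n+1). Taking planned doses as duration/21 unrounded gives 21n/(21n+1). Counting by cycle, or rounding that quotient down, gives n/n = 100%. Rounding it up gives the same result as the date count.

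| Doses n | SAP days | 21n | Absolute, % of correct | Atezolizumab mg/week | Relative, date count | Relative, unrounded quotient |
|---|---|---|---|---|---|---|
| 1 | 22 | 21 | 95.5 | 381.8 | 50.0% | 95.5% |
| 2 | 43 | 42 | 97.7 | 390.7 | 66.7% | 97.7% |
| 4 | 85 | 84 | 98.8 | 395.3 | 80.0% | 98.8% |
| 10 | 211 | 210 | 99.5 | 398.1 | 90.9% | 99.5% |
| 70 | 1471 | 1470 | 99.9 | 399.7 | 98.6% | 99.9% |

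**Patients off schedule (4 doses, due dates counted).** If the calendar rolls forward from the last dose, the SAP window always holds 5 due dates and the corrected window 4. If the calendar is fixed from Cycle 1 Day 1:
- last dose 1 or 3 days early: 4 due dates with either formula;
- last dose on time: 5 with the SAP formula, 4 with the corrected one;
- last dose 1, 3 or 7 days late: 5 with either formula.

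**The case against.** The certain effect is small. Protocol Table 5-1 allows 3 days either way, and under Protocol 5.3 a dose "may be delayed by up to 7 days to recover from previous Aes", so ordinary scheduling moves a patient's figure by more than one day. SAP 10.0 rules out formal testing. The maximum tolerated dose is determined from dose-limiting toxicity rates (Protocol 5.4.6.1), and no threshold in either document uses dose intensity. All of this stands and limits the importance of the point. It does not make the formula correct: scheduling variation reflects what happened to the patient, while the extra day is a fixed error in one direction.

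A reader might infer that the plan will report relative dose intensities of 50%, 67% and 80% for compliant patients after 1, 2 and 4 doses, and that every patient acquires a phantom planned dose because of the added day. The documents do not support that. SAP 8.7.5 sets no counting algorithm. The visit schedule has one dose per cycle and SAP 10.3.1 already summarises cycles started, so a count by cycle is available and gives 100%. On a calendar fixed from Cycle 1 Day 1, the extra dose does not arise when the last dose is early. When the last dose is late, it arises with or without the added day. The larger discrepancy is therefore a possible result of an undefined count, and the added day is only one contributor to it.

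**Conclusion.** Wrong as written; minor, descriptive effect. SAP 8.7.1 overcounts by exactly one day for each patient and drug, and the same day enters the combined duration in the combination arm. For on-schedule patients, absolute dose intensity is understated by 1/(21n+1): 4.5% after 1 dose, 2.3% after 2, 1.2% after 4 and under 0.5% from 10 doses on. This rests only on the stated formula and the 21-day cycle.

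For relative dose intensity the conclusion is conditional. An on-schedule patient's value is n/(n+1) if due dates are counted literally and 95.5% to 100% under the other readings (unrounded quotient, rounding down, count by cycle). The SAP does not choose between them, so the defect there is a missing definition and no single wrong number can be attributed to it. No dose-escalation rule or test result is affected.

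**What to change.** Make two edits to the SAP.

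1. In 8.7.1, define duration in weeks as (last dose date − first dose date + 21)/7, for each drug and for the combined duration. On-schedule patients then have 3n weeks, and atezolizumab returns 400 mg/week.

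2. In 8.7.5, state that scheduled administrations are counted by cycle from the first through the last dose, including any skipped in between. A patient dosed in Cycles 1 and 3 with Cycle 2 skipped has 3 scheduled and 2 given, so 66.7% at full dose; an on-schedule patient has 100%.

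Do not define planned doses as duration/3 weeks rounded down. Two full doses with the second one day early, which is inside the permitted window, give 20 + 21 = 41 days; 41/21 rounds down to 1 planned dose and a relative dose intensity of 200%. Four doses with the last one day early give 62 + 21 = 83 days, 3 planned doses and 133%.

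The cost is one formula, one clarifying sentence and the matching programming. No data collection or dosing changes, and SAP 4.0 provides for an updated version to be approved before database lock.
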